9.2.2 Study population

The data will be retrospectively abstracted from the medical chart after eligibility assessment. Eligible patients will be categorized into the cohort A (patients treated with Tio + Olo), B (patients treated with other LABA/LAMA therapy), and C (patients treated with LAMA therapy).

Inclusion criteria

Patients who fulfil **ALL** the following criteria are included.

1. Patients who diagnosed with COPD who were prescribed with LABA/LAMA (FDC or free combo) as a new initiation or switching from other therapy (i.e., single/dual/triple), or newly receiving LAMA treatment for 3 months at least prior to 30 June 2018
2. Male or female patients ≥ 40 years of age

Exclusion criteria

Patients who meet the following criterion are not included.

1. Patients with documented diagnosis of bronchial asthma, asthma-COPD overlap syndrome (ACOS), bronchiectasis, cystic fibrosis, or lung cancer

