9.2.3 Study visits

The abstracted data will be recorded on the case report form (CRF). **Table 1** shows the collected data at different retrospective period of the medical chart.

Table 1 Data collection schedule

| Variables | Time points | Eligibility assessment | Data collection retrospectively | | |
|----------------------------------|-------------|------------------------|---------------------------------|-------------------------|--------------------------------------|
| | | | Before the index date | Index date [#] | 1-year follow-up period [†] |
| Eligibility assessments | X | | | | |
| Demographics ¹ | | | | X* | |
| Diagnosis of COPD ² | | | | X* | |
| Smoking status ³ | | | | X* | |
| Comorbidity ^{4, §} | | X [◊] | X | X | |
| COPD assessments [‡] | | | | | |
| CAT ⁵ | | X ^Δ | X | X | |
| mMRC ⁶ | | X ^Δ | X | X | |
| Examinations [‡] | | | | | |
| Spirometry data ⁷ | | X ^Δ | X | X | |
| Eosinophils | | X ^Δ | X | X | |
| Records [‡] | | | | | |
| Acute exacerbations ⁸ | | X ^{&} | X | X | |
| Hospital admissions ⁹ | | X ^{&} | X | X | |
| Treatments | | | | | |

| Variables | Time points | Eligibility assessment | Data collection retrospectively | | |
|--|-------------|------------------------|---------------------------------|-------------------------|--------------------------------------|
| | | | Before the index date | Index date [#] | 1-year follow-up period [†] |
| Related to COPD ^{10, \$} | | | X ^{11, ♦} | X | X |
| Related to comorbidities ^{12, \$} | | | X [◊] | X | X |
| Rescue treatments ^{13, ‡} | | | X [◊] | X | X |
| Oxygen therapy ^{14, \$} | | | X [◊] | X | X |
| Others ^{15, \$} | | | X [◊] | X | X |

[#]Not later than 30 June 2018; defined as the date of COPD patients in the cohort A and B starting using LABA/LAMA therapy regardless of new initiation or switching from other single/dual/triple treatment, or the date of the patients in the cohort C starting using LAMA treatment

[†]Not later than 1 year after the index date

^{*}The data nearest to the index date will be collected.

[◊]The data 6 months before the index date will be documented.

^{\$}The data will be collected every 6 months (allowed window: ± 1 month).

[‡]All available data on the medical chart will be recorded.

[△]The data nearest to the index date will be collected as the **Baseline**.

[&]The data/events ever since patients started receiving LABA/LAMA or LAMA therapy will be collected (maximum: trace back to 1 year before the index date).

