9.3.2 Outcomes

9.3.2.1 Primary outcomes

- Time to the first moderate or severe COPD exacerbation

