9.3.2.2 Secondary outcomes

- Annualized rate of mild/moderate/severe exacerbation
- Time/reason (e.g., severe airflow limitation, diagnosis of asthma, worsening exacerbation) from LABA/LAMA escalating to LABA/LAMA/ICS or from LAMA to dual therapy

Proprietary confidential information © 2019 Boehringer Ingelheim International GmbH or one or more of its affiliated companies

- Percentage of patients receiving LABA/LAMA switched to triple therapy or LAMA switched to dual therapy
- Change in pulmonary function after LABA/LAMA or LAMA initiation
- Use of rescue medications

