9.3.3.3 Acute exacerbation of COPD

The data from 1 year before the index date until death or 1 year after the index date should be collected.

Acute exacerbation is defined as a complex of lower respiratory events/symptoms (worsening or new onset) related to the underlying COPD, with a duration of 3 days or more, requiring a prescription of antibiotics and/or systemic steroids and/or hospitalization (should all be accompanied by code of ICD-9-491.21 or ICD-10-J44.1). Within the retrospective period, the onset/stop date of COPD exacerbation, severity* (mild, moderate, severe), and its outcome (leading to hospitalization/acute respiratory failure [ICD-9-518.81 or ICD-10-J96.00/J96.01/J96.02] or not) will be recorded. In terms of the exacerbation-related therapies, they will be recorded onto the page of “Rescue treatments” in the CRF.

***Mild exacerbation** is a patient with worsening but self-managed symptoms.

Moderate exacerbation is a patient receiving an exacerbation-related prescription such as oral corticosteroid (prednisone or prednisolone) and/or antibiotic, but not requiring hospitalization.

Severe exacerbation is a patient requiring hospitalization or emergency room visit due to COPD (ICD-9-491.21 or ICD-10-J44.1).

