9.7.1 Main analysis

The propensity score matching approach* will be used to balance the baseline characteristics between the study cohorts. These data will be compared descriptively between patients receiving different regimens (Tio + Olo vs. other LABA/LAMA vs. LAMA). If the propensity score matching is done, the difference before and after matching will be considered both.

For the primary outcome

Time to the first moderate or severe COPD exacerbation will be compared between different cohorts using Kaplan-Meier curves with the incidence and time to events, and statistical significance will be assessed using log-rank tests.

Time to first acute exacerbation starts from the index date to the date of the first acute exacerbation recorded on the CRF. Patients with exacerbation free at the time of escalating to ICS or no documented with exacerbations will be censored.

For secondary outcomes

- Time to escalating to dual/triple therapy will also be analysed using Kaplan-Meier curves and log-rank tests.
- The annualized rate of exacerbation with various severity will be calculated for each study group (episodes/patient-year), and the differences between the three cohorts will be compared by rate ratio.
- Results of lung function (i.e., spirometry data) and COPD assessments (i.e., CAT and mMRC) will be evaluated by the change from baseline. Pair *t*-test or other applicable statistical methods will be used for assessing the intra-group difference under a significance level of 0.05.
- Chi-square test or Fisher's exact test will be applied for categorical variables such as reasons for switching/escalating therapies, frequency, and percentage, etc.

*NOTE: Variables may include but not limited to age, gender, disease duration before index date, smoking status, body mass index, COPD assessment score (e.g., CAT and mMRC), spirometry data (e.g., FEV₁), oxygen therapy, comorbidities, disease severity, previous exacerbation, previous treatments, or eosinophil counts, where appropriate.

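### The primary event rule does not require onset after the index date, so an exacerbation that prompted the index prescription can be counted as a day-0 outcome

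*Combined protocol and SAP*

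**What the plan says.** - **Primary outcome (Section 9.3.2.1):** "Time to the first moderate or severe COPD exacerbation".
- **Timing rule (Section 9.7.1):** "Time to first acute exacerbation starts from the index date to the date of the first acute exacerbation recorded on the CRF". This is the only readable rule on which episode is the event and when it is dated.
- **What is on the form (Section 9.3.3.3):** "The data from 1 year before the index date until death or 1 year after the index date should be collected". Table 1 in Section 9.2.3 marks acute exacerbations and hospital admissions for collection before the index date, on the index date and during follow-up.
- **Dates and duration (Section 9.3.3.3):** the form holds "the onset/stop date of COPD exacerbation", and an episode is one "with a duration of 3 days or more". One episode can therefore straddle the index date.
- **Entry (Section 9.2.2):** COPD, the qualifying treatment for the required period, and age. The single exclusion lists other diagnoses. Cohorts A and B may enter "as a new initiation or switching from other therapy (i.e., single/dual/triple"); cohort C may enter only on a newly started LAMA.
- **Treatment changes at admissions:** Table 1 (note 9) and Section 9.3.3.2 (item 4) have the form record why medication was switched at admissions for COPD exacerbation, reaching back 1 year before index.
- **Follow-up:** the Abstract (study design) starts each patient's follow-up at the index date.

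**The concern.** An exacerbation visit or admission is a natural moment to start or change maintenance treatment, and nothing at entry keeps such patients out. If that episode is dated at the index visit, the timing rule accepts it as the primary event at time zero. The event then preceded and caused the prescription, yet it is analysed as a failure of the prescribed drug.

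The text also leaves the event date open. If it is the onset date, a prompting episode that began before index has no valid event time. The plan does not say whether to set it to day 0, drop it, or move to the next episode. Two competent programmers could obtain different primary results from the same database.

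Propensity score matching does not resolve this. Section 9.7.1 lists previous exacerbation only as a possible matching variable, and a covariate does not decide which episode counts as the outcome. At stake are the size of the primary contrast and, if the share of such episodes differs between cohorts, its direction.

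**Working it through.** **The plan's own figures.** No figure in the protocol concerns episodes at index. The only planning figure is Table 2 in Section 9.5: rates of 0.78 and 0.90 per patient-year, ratio 0.78/0.90 = 0.867, with 95% CI 0.768 to 0.978 for 300 versus 800 patients. With exposure PY per patient, the Poisson interval is 0.867 × exp(±1.96 × √(1/(0.78 × 300 × PY) + 1/(0.90 × 800 × PY))). The stated 2 patient-years give 0.781 to 0.962; the printed limits appear at 1.5. That mismatch is a separate matter. Only the rates and cohort sizes are used below.

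**Assumptions.** Constant rates; 1-year follow-up; no other censoring; no matching; two-sided 5% log-rank test (Section 9.7.1 states 0.05 only for within-group tests). A share q of a cohort has an index episode counted at day 0. The documents give no value for q, so it is varied from 0% to 20%.

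**One-year risk.** Risk = 1 − (1 − q) × exp(−rate).

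- q = 0: 1 − exp(−0.78) = 54.2% and 1 − exp(−0.90) = 59.3%.
- q = 10% in both: 0.10 + 0.90 × 0.542 = 58.7% and 0.10 + 0.90 × 0.593 = 63.4%.

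**Simulated log-rank test,** 300 versus 800 patients, 3,000 runs per row.

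*Equal shares, true hazard ratio 0.867:*

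| q in both cohorts | Estimated HR | Power |
|---|---|---|
| 0% | 0.87 | 35% |
| 5% | 0.88 | 31% |
| 10% | 0.89 | 28% |
| 20% | 0.90 | 24% |

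Cross-check of the first row: expected events are 300 × 0.542 + 800 × 0.593 ≈ 637. The Schoenfeld formula with allocation 300/1100 then gives 36% power.

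*Unequal shares, true hazard ratio 1 (rate 0.90 in both):*

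| q, first vs second cohort | Estimated HR | False rejection |
|---|---|---|
| 0% vs 0% | 1.00 | 4.6% |
| 5% vs 10% | 0.92 | 15% |
| 10% vs 5% | 1.09 | 17% |
| 5% vs 15% | 0.86 | 45% |
| 15% vs 5% | 1.19 | 49% |
| 10% vs 20% | 0.86 | 44% |
| 20% vs 10% | 1.19 | 49% |

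Equal shares dilute the effect modestly. A 10-point difference in shares produces an apparent effect about as large as the planned 0.87, in either direction.

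**The case against.** The strongest reply is that this is a narrow ambiguity. Much of it stands and sets the limits of the point.

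- **Resolved earlier episodes.** Because the form reaches back a year, a reader might infer that any earlier exacerbation becomes the outcome. The documents do not support that: the clock and follow-up both start at index, so such an event would have negative time. Section 9.3.3.2 treats earlier exacerbations as history. Only the literal wording needs correcting.
- **Not every prompted start gives a day-0 event.** With a strict onset date, an episode that began before index falls outside the clock. A day-0 event needs the episode to be dated at the index visit, for example when the visit date is entered as onset. Since the plan does not choose the date, the exposure remains.
- **Evidence that such starts occur.** A reader might cite the secondary outcome "Time/reason (e.g., severe airflow limitation, diagnosis of asthma, worsening exacerbation) from LABA/LAMA escalating to LABA/LAMA/ICS or from LAMA to dual therapy". That concerns leaving the study treatment after index and gives no reason for starting it. The better support is the recording of switching reasons at exacerbation admissions. It shows that such changes are anticipated, not how often they coincide with the index date.
- **Which comparison is asymmetric.** A reader might infer that the entry rules favour A over B or the reverse. A and B have the same entry rules; the asymmetry is A and B against C. The simulation uses the A and B planning sizes and rates only to show scale.
- **Broad entry is deliberate.** Section 9.9 says so, and the fix leaves entry unchanged.
- **Redaction.** The contents list shows a redacted entry between 9.7.1 and 9.7.3, so a sensitivity analysis cannot be called absent with certainty. The primary definition in 9.7.1 is readable and incomplete regardless.

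**Conclusion.** The point holds in this form: as written, the primary event rule lets an episode that prompted the index prescription, and is dated at the index visit, count as a day-0 outcome. This goes beyond missing detail, because following the stated rule can bias the primary result.

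The size cannot be read from the documents. If the share of such episodes is equal across cohorts at 5% to 20%, the effect is modest: a hazard ratio of 0.87 becomes about 0.88 to 0.90. If the shares differ by 10 points, a true hazard ratio of 1 becomes about 0.86 or 1.19. These results rest on assumed shares, constant rates and an unmatched comparison. Whether an imbalance exists, and in which direction, is unknown. The entry rules give a reason to expect one only between A or B and C.

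**What to change.** In Section 9.7.1:

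1. Define the primary event as the first moderate or severe exacerbation whose onset date is after the index date. This names the date used and restores the severity restriction missing from the timing sentence.
2. Classify any episode with onset on or before the index date, including one still ongoing then, as baseline history.
3. State that a continuation of such an episode is not a new event.
4. Add one sensitivity analysis leaving out patients with an episode ongoing at the index date.

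The cost is a few sentences and one extra run. Onset and stop dates are already collected. The downside is that a few exacerbations that truly began on the index date will not be counted.

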| Study design: | 
This is a retrospective, multi-center, cohort study to collect the data on COPD patients who were administered with LABA/LAMA (FDC or free combo) or LAMA treatment for 3 months at least prior to 30 June 2018. For LABA/LAMA therapy, new initiation or switching from other therapy (i.e., single/dual/triple) are both acceptable; for LAMA
 | | |

Proprietary confidential information © 2019 Boehringer Ingelheim International GmbH or one or more of its affiliated companies

| | |
|--------------------|---|
| | 
treatment, only new initiation will be acceptable. The data abstracted from eligible patients will be recorded only when they are available in the medical chart and will be categorized into the cohort A (patients treated with Tio + Olo), B (patients treated with other LABA/LAMA therapy), and C (LAMA therapy).
 
The follow-up period for each patient will be from the index date* until the date of death or 1 year after the index date, whichever occurs first. Patients will be censored at the time from one LAMA/LABA or LAMA switched to another LAMA/LABA or ICS.
 
*Index date: It is defined as the date of COPD patients in the cohort A and B starting using LABA/LAMA therapy regardless of new initiation or switching from other single/dual/triple treatment, or the date of the patients in the cohort C starting using LAMA treatment.
 |
| Population: | 
This study plans to review the medical chart from approximately 1,800 COPD patients receiving LABA/LAMA or LAMA treatment for 3 months at least prior to June 30 2018 in Taiwan.
 
Inclusion criteria
 
Patients who fulfil ALL the following criteria are included.
 
1. Patients who diagnosed with COPD who were prescribed with LABA/LAMA (FDC or free combo) as a new initiation or switching from other therapy (i.e., single/dual/triple), or newly receiving LAMA treatment for 3 months at least prior to 30 June 20182. Male or female patients ≥ 40 years of age 
Exclusion criteria
 
Patients who meet the following criterion are not included.
 
1. Patients with documented diagnosis of bronchial asthma, asthma-COPD overlap syndrome (ACOS), bronchiectasis, cystic fibrosis, or lung cancer |

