The hospitalization caused by COPD exacerbation (ICD-9: 491.21; ICD-10: J44.1) should be documented on the CRF, including admission/discharge date, treatments (doses, frequency, and the route of administration), and reasons for switching medications. Other hospitalizations unrelated to COPD exacerbation will not be recorded.

5. Laboratory data: eosinophils

The data nearest to the index date will be collected as the **Baseline** and will continue recording until death or 1 year after the index date.

Blood eosinophil counts are used for a standard of applying ICS treatment for patients with $\geq 2\%$ eosinophil counts.⁶ Additionally, higher blood eosinophils may incur greater exacerbations in patients treated with LABA only (without ICS).^{19,20} Eosinophils counts and assessment date will be recorded.

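### Censoring the primary outcome at escalation to ICS may be informative, and the visible plan sets no as-started analysis beside it

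*Combined protocol and SAP*

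**What the plan says.** Section 9.7.1 (primary outcome) compares cohorts by Kaplan-Meier curves, and "statistical significance will be assessed using log-rank tests". Its censoring rule is: "Patients with exacerbation free at the time of escalating to ICS or no documented with exacerbations will be censored".

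The Abstract (Study design) gives a wider rule: "Patients will be censored at the time from one LAMA/LABA or LAMA switched to another LAMA/LABA or ICS". The visible text of neither place names stopping the inhaler or stepping down as a censoring event.

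On why patients escalate, section 9.3.2.2 lists as a secondary outcome "Time/reason (e.g., severe airflow limitation, diagnosis of asthma, worsening exacerbation) from LABA/LAMA escalating to LABA/LAMA/ICS or from LAMA to dual therapy". Section 9.3.3.2 adds "Blood eosinophil counts are used for a standard of applying ICS treatment", and goes on to say that higher counts may go with more exacerbations in patients on LABA without ICS.

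On data, section 9.3.3.3 says of exacerbations: "The data from 1 year before the index date until death or 1 year after the index date should be collected". Collection does not stop at escalation. The Abstract defines follow-up in the same way: "The follow-up period for each patient will be from the index date* until the date of death or 1 year after the index date".

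The contents list shows a redacted entry between 9.7.1 and 9.7.3.

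**The concern.** Kaplan-Meier and log-rank are valid under censoring only if patients removed at a given time have the same later risk as comparable patients still followed. Two of the three example reasons for escalation, airflow limitation and worsening, point to higher risk, and so does the eosinophil link. A mild exacerbation is not a primary event, so a patient escalated after one can be censored before an event is counted.

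If the cohorts escalate at different rates, part of any difference between the primary curves could then reflect how readily physicians add ICS and not how well the starting regimen prevents exacerbations. Propensity matching on baseline variables does not remove selection that happens after the index date. The study is looking for a small difference (an assumed rate ratio of 0.87 in section 9.5), so even a modest bias counts.

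**Working it through.** **Yardstick from the plan.** The plan gives no figure for this censoring. Section 9.5 assumes 0.78 and 0.90 exacerbations per patient-year; 0.78/0.90 = 0.867, which reproduces the stated ratio of 0.87, and ln(0.867) = -0.143. The confidence intervals in Table 2 are not used here.

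**Who is affected.** Only patients without a moderate or severe exacerbation at escalation are censored by it. Those escalated because of such an event already count as events. The bias can come only from escalation for symptoms, airflow limitation, mild events, eosinophils or similar reasons.

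**Check 1: 12-month incidence, closed form.** Assumptions: first-event hazard 0.84·Z per year (0.84 is the midpoint of 0.78 and 0.90); Z is gamma with mean 1 and variance 1; escalation hazard e·Z; ICS has no effect on risk.

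- True incidence: 1 - 1/(1 + 0.84) = 45.7%.
- Kaplan-Meier with censoring at escalation: 1 - (1 + 0.84 + e)^(-0.84/(0.84 + e)).
- Share censored by escalation: e/(1 + 0.84 + e).

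If escalation can start only after month 3 (one reading of the three-month treatment requirement in section 9.2.2), the cumulative hazard becomes ln(1.21) + [0.84/(0.84 + e)]·ln[(1.84 + 0.75e)/1.21], where 1.21 = 1 + 0.84 × 0.25. The steeper case, escalation hazard e·Z², was integrated numerically.

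| e | Linear, from day 0 (share censored) | Linear, after month 3 | Squared, from day 0 |
|---|---|---|---|
| 0.1 | 44.7% (5%) | 45.2% (3%) | 43.4% (7%) |
| 0.3 | 42.9% (14%) | 44.3% (9%) | 40.3% (17%) |
| 0.6 | 40.6% (25%) | 43.0% (16%) | 37.2% (26%) |

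Gap between two cohorts of equal true risk, one at e = 0.1 and one at e = 0.6:

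- linear, after month 3: 45.2 - 43.0, about 2 points;
- linear, from day 0: 44.7 - 40.6, about 4 points;
- squared, from day 0: 43.4 - 37.2, about 6 points.

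**Check 2: hazard ratio, simulation.** Truth is 1.00; the ratio is the more-escalating cohort against the less-escalating one; simulation noise is about 0.01. The frailty model uses an exacerbation hazard of 0.8 per year, log-normal frailty with SD up to 1.0, and escalation after month 3 at 0.60 against 0.15 per year, multiplied by frailty^g. The worsening-state model has three-month spells that multiply the hazard by 3 or 5 and lead to ICS with probability 0.4 or 0.6 in one cohort and 0.1 in the other. ICS either has no effect or cuts the later hazard by 25%.

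| Scenario | Share censored | HR under 9.7.1 |
|---|---|---|
| Escalation unrelated to risk (g = 0) | 23-25% vs 7% | 0.99-1.01 |
| Risk-driven frailty, g = 0.5 | 19-22% vs 5-6% | 0.97-1.00 |
| Risk-driven frailty, g = 1 | 17-21% vs 5-6% | 0.96-0.98 |
| Worsening state | 11-18% vs 3% | 0.93-0.98 |
| Lower-risk patients escalate (g = -1) | 29-44% vs 9-19% | 1.02-1.08 |

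Against the assumed effect, HR 0.98 is ln(0.98)/(-0.143) = 14% of the log ratio, and HR 0.93 is ln(0.93)/(-0.143) = 51%. In the risk-driven frailty scenarios with 300 and 800 patients, the log-rank test rejects in about 4-8% of data sets (nominal 5%).

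**Check 3: the as-started analysis in the same simulations.** Following everyone for the full year gives an HR of about 1.00 when ICS has no effect, and about 0.96-0.99 when ICS cuts the later hazard by 25%.

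**The case against.** A reader might infer that the rule biases every curve downwards and always flatters the cohort that escalates more. The documents do not support that. The reasons in section 9.3.2.2 are examples, one of them (a diagnosis of asthma) is not worsening, and no escalation rates are given. Both direction and size depend on who escalates.

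A reader might also infer that the year of exacerbation data is wasted. Patients who do not escalate contribute all of it; only data after escalation go unused in the primary analysis.

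Nor is the as-started analysis simply the unbiased one. It answers a different question: outcome after starting a regimen, including whatever is added later. If ICS works, it too favours the cohort that escalates more, as check 3 shows. Choosing which analysis leads is a choice of question, so replacing the main analysis is not required.

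Three further objections carry weight. The larger figures in check 1 use strong assumptions: frailty variance 1, escalation tied exactly to risk, and a six-fold contrast in escalation. Censoring weights would need CAT, mMRC and spirometry over time, which are recorded only where charted, with imputation barred (9.7.3). And time to escalation and the percentage escalating are secondary outcomes, so a difference between cohorts would be seen.

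What remains is that seeing different escalation does not show how far it moved the primary curves, and the visible text offers nothing that would. The redacted section could contain such an analysis; the main rule in 9.7.1 stands either way.

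**Conclusion.** The concern holds in conditional form. The protocol's own text makes censoring at ICS escalation potentially informative, and the visible plan gives no way to judge its effect although the data will be in hand. If risk drives escalation and the cohorts escalate at different rates, the bias with no true difference is roughly HR 0.93 to 1.00, or about 2 to 6 percentage points at 12 months. That is modest, but not negligible against an assumed ratio of 0.87. The frailty, the link between risk and escalation, its timing and the escalation shares are all assumptions, and none comes from the documents. The sponsor should make the change; the point does not invalidate the design.

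**What to change.** In section 9.7.1:

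1. Keep the censored analysis and report beside it an as-started analysis by index cohort, from the index date to the first moderate/severe exacerbation, with follow-up to death or 1 year and no censoring at switch, escalation or stopping. State how death before an exacerbation is handled.
2. Show the number and timing of patients censored at escalation, by cohort.
3. Say which question each analysis answers, and draw a cohort conclusion only where the two agree.
4. Treat inverse-probability-of-censoring weighting as optional, where chart data allow.
5. Reconcile the censoring lists in the Abstract and 9.7.1. They differ on a move to another LABA/LAMA, which decides how LAMA-cohort patients who move to LABA/LAMA are handled.

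Items 1 to 3 and 5 cost protocol wording and one further analysis of data already collected. Weighting would cost more. The downside is that the as-started result includes any effect of the added ICS and dilutes differences if many patients cross over, which is why both analyses should be shown.

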4. ABSTRACT

| | | | |
|---|--|---------------------------------|---|
| Name of company: Boehringer Ingelheim | | | |
| Name of finished medicinal product: Spiolto® (tiotropium/olodaterol) | | | |
| Name of active ingredient: tiotropium/olodaterol (ATC code: R03AL06; long-acting bronchodilators; a muscarinic receptor antagonist for tiotropium and a β adrenoreceptor agonist for olodaterol) | | | |
| Protocol date: 18 June 2019 | Study number: 1237-0086 | Version/Revision: 1.0 | Version/Revision date: 25 November 2019 |
| Title of study: | Taiwan Outcomes and Real-world Treatment Options for Chronic Obstructive Pulmonary Disease | | |
| Rationale and background: | 
Recently, more and more randomized controlled trials (RCT) demonstrated effectiveness of dual bronchodilators for the treatment of chronic obstructive pulmonary disease (COPD). DYNAGITO trial¹ has provided further evidences for tiotropium + olodaterol (Tio + Olo) compared with tiotropium in reducing moderate/severe exacerbations. In the real-world setting in Taiwan, the medication environment and electronic medical charts are well-established in medical centers. Hence, retrospective analysis is fully possible. Boehringer Ingelheim (BI) Taiwan and clinical practitioners' common goal are to adopt optimal treatment for COPD patients diagnosed per GOLD guideline.
 
So far, we can refer to some head to head studies examining the impact on lung function of various LABA/LAMA combinations; however, there is no study observing real world outcomes on prevention/risk reduction of acute exacerbations in Taiwan. The extent of outcomes from Tio + Olo (Spiolto®), other LABA/LAMA fixed-dose combinations [FDC]/free combos, or LAMA treatment of benefit for COPD patients in reducing acute exacerbation, is of great interest to explore.
 | | |
| Research question and objectives: | 
The primary objective is to understand the occurrence of COPD exacerbations in patients treated with LABA/LAMA or LAMA in the routine clinical practice in Taiwan.
 
The secondary objectives are to realize the clinical characteristics and prescription patterns for the COPD population in Taiwan.
 | | |

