9.5 STUDY SIZE

Based on the projected market share and per physician's clinical experience, data from approximately 1,800 patients will be collected.

Among these patients, using Tio + Olo FDC versus other LABA/LAMA therapy (FDC or free combo) is assumed the ratio of 1:2 (~ 300 Tio + Olo, ~ 800 other LABA/LAMA therapy). If we assume the same annualized event rates as in the Taiwanese subgroup analysis report of DYNAGITO¹ (i.e. 0.78 per patient-year for Tio + Olo and 0.90 per patient-year for other

therapies), expecting the 95% CI for incidence rate ratio to be 0.87 (0.768, 0.978), with good precision. The following **Table 2** also shows that with smaller sample size, the precision is reduced (wider 95% CI).

Table 2 Sample size estimation

| Tio + Olo | | Other | | Incidence rate ratio (95% CI) |
|---------------------|-------------|---------------------|-------------|-------------------------------|
| True Incidence rate | Sample size | True Incidence rate | Sample size | |
| 0.78 | 300 | 0.90 | 800 | 0.87 (0.768, 0.978) |
| 0.78 | 300 | 0.90 | 300 | 0.87 (0.751, 1.000) |
| 0.90 | 300 | 0.97 | 800 | 0.93 (0.829, 1.039) |
| 0.90 | 300 | 0.97 | 300 | 0.93 (0.810, 1.062) |
| 0.90 | 200 | 0.97 | 200 | 0.93 (0.786, 1.094) |
| 0.90 | 200 | 0.97 | 100 | 0.93 (0.734, 1.173) |

In this table, it is assumed that all patients have on average ~ 2 patient-year exposure.

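### The expected rate-ratio interval in section 9.5 is not tied to a named outcome: the rate outcome is worded by severity, and a combined moderate-or-severe rate is not named

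*Combined protocol and SAP*

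**What the plan says.** Section 9.5 takes its rates from the cited randomised trial: "If we assume the same annualized event rates as in the Taiwanese subgroup analysis report of DYNAGITO". The figures are "0.78 per patient-year for Tio + Olo and 0.90 per patient-year for other" therapies, with cohorts of about "300 Tio + Olo, ~ 800 other LABA/LAMA therapy". The result is stated as "expecting the 95% CI for incidence rate ratio to be 0.87 (0.768, 0.978), with good precision". No severity class is attached to the rates. The only hint is in the abstract's rationale, which describes the cited trial's result for Tio + Olo as "compared with tiotropium in reducing moderate/severe exacerbations".

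The rate outcome in 9.3.2.2 is "Annualized rate of mild/moderate/severe exacerbation". The analysis in 9.7.1 reads "The annualized rate of exacerbation with various severity will be calculated for each study group (episodes/patient-year", with the three cohorts then compared by rate ratio. The abstract says the same. The primary outcome in 9.3.2.1 does combine moderate and severe events, but it is analysed only as time to first event, and no precision or power is given for it.

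**The concern.** Table 2 is the only quantitative support for the study size, and it describes a rate ratio that no listed outcome clearly matches. If the rate ratios are reported separately for mild, moderate and severe events, each rests on fewer events than Table 2 assumes and has a wider interval. A reader of 9.5 could carry the claim of good precision over to ratios that do not have it.

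The unsettled wording also leaves several possible rate ratios (each severity, all severities pooled, moderate plus severe) with none designated as the main one. The ratio that shares the primary event definition, and is more precise than either the moderate or the severe ratio alone, might not be reported.

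**Working it through.** **Inputs.** From 9.5 and Table 2: rates 0.78 and 0.90, cohorts 300 and 800, stated exposure about 2 patient-years, printed interval (0.768, 0.978). From 9.1: follow-up ends at death or 1 year after the index date. The split of events by severity is not in the documents and is assumed below. (The text of 9.5 says the allocation "is assumed the ratio of 1:2", but 300:800 is 1:2.67; Table 2 uses 300 and 800, and so does this check.)

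**Formula.** Poisson log rate ratio with a Wald interval. Events E = rate × n × years; SE = √(1/E₁ + 1/E₂); interval = (0.78/0.90) × exp(±1.96 × SE). The ratio is 0.8667 and its logarithm is −0.143.

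**Reproducing the printed interval.**

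| Years per patient | Events | SE | Interval |
|---|---|---|---|
| 2 (as stated) | 468 vs 1440 | 0.0532 | 0.781 to 0.962 |
| 1.5 | 351 vs 1080 | 0.0614 | 0.768 to 0.978 |
| 1 (follow-up cap) | 234 vs 720 | 0.0752 | 0.748 to 1.004 |

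The printed limits imply SE = ln(0.978/0.768)/(2 × 1.96) = 0.0617. They match 1.5 patient-years, not the stated 2. The first five rows of Table 2 all imply about 1.5 years (1.49 to 1.51), and the sixth about 1.1.

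**Effect of splitting by severity.** If a class holds a share s of the events in both cohorts and has the same ratio, its SE is the full SE divided by √s. Using the 1.5-year counts, which reproduce the printed interval, and the 1-year cap:

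| Assumed share | Interval at 1.5 years | Interval at 1 year |
|---|---|---|
| 100% | 0.768 to 0.978 | 0.748 to 1.004 |
| 80% | 0.757 to 0.992 | 0.735 to 1.022 |
| 50% | 0.731 to 1.028 | 0.704 to 1.068 |
| 20% | 0.662 to 1.134 | 0.623 to 1.205 |

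**Share needed to exclude 1.** The upper limit reaches 1 when s = (1.96 × full SE / 0.143)². With the printed SE this is (1.96 × 0.0617 / 0.143)² ≈ 0.71. At the stated 2 years it is 0.53; at 1 year it is 1.06, which no class can reach.

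**Consequence for two classes.** If 0.78 and 0.90 count at least the moderate and severe events, those two shares add to at most 100%. They cannot both exceed 71%, nor both exceed 53%. So at least one of the two expected intervals includes 1 at 1, 1.5 or 2 years, whatever the actual split.

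**The case against.** The strongest reply is that the wording does not commit the plan to separate ratios only. A slash between severities can mean pooled as easily as separate, 9.7 also plans to summarise exacerbation rates without mentioning severity, and a redacted entry stands between 9.7.1 and 9.7.3 in the table of contents. A reader might infer that no planned rate ratio has the event count behind the printed interval because of the severity split. The documents do not support that: a pooled or moderate-plus-severe ratio is not excluded.

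A reader might also infer that a pooled rate could not be the rate that was sized, since it would include mild episodes. That does not follow either. Section 9.3.3.3 requires antibiotics, systemic steroids or hospitalization for an event to count, while calling a mild event self-managed, so few mild events may qualify and a pooled rate may be close to moderate plus severe. Nor does 9.5 say that its rates are moderate-or-severe; that is only suggested by the abstract.

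It is also fair that 9.5 states no power or hypothesis test, that it bases the 1,800 patients on market share and clinical experience, that only one of Table 2's six rows excludes 1, and that the rate is a secondary outcome. Finally, the shortfall that can be shown without assuming severity shares comes from exposure: at the 1-year cap the full event count already gives an upper limit of 1.004.

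These replies limit the claim but leave its core. The severity class of the sized rates is unstated, the combined rate is not named, and any single-severity ratio is less precise than the combined one. The exposure problem adds to the loss from splitting; it does not replace it.

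**Conclusion.** The point holds as a gap in specification: section 9.5 gives an interval for a rate of unstated severity, and the rate outcome does not name the combined moderate-or-severe rate. It does not show that the interval belongs to no planned ratio.

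On size, taking the printed interval at face value, a class needs more than about 71% of events for its expected interval to exclude 1, so the moderate and severe ratios cannot both do so. This rests on Poisson variation, the same ratio and the same shares in both cohorts, and rates that count at least moderate and severe events. The intervals at particular shares are illustrations. The face-value figures are optimistic, because the printed interval needs 1.5 patient-years and follow-up allows at most 1. Death and the censoring at treatment switch (abstract, study design) shorten exposure further, and matching may reduce the numbers. The primary time-to-event analysis is not affected.

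**What to change.** 1. In 9.3.2.2, 9.7.1 and the abstract, name the annualized rate of moderate or severe exacerbations combined, with the primary outcome's event definition, as the main rate comparison. Keep the severity-specific rates as supportive.
2. In 9.5, state which severities 0.78 and 0.90 count. Recompute Table 2 at no more than 1 year of exposure, then say that it refers to the combined rate. Linking the table unchanged would attach an unattainable interval to the newly named comparison: the full event count at 1 year gives 0.748 to 1.004, and an assumed 50% share gives 0.704 to 1.068.
3. Limit the claim of good precision to the combined rate, and only as far as the recomputed table supports it. Showing the severe-only interval over a range of assumed shares would tell readers what to expect there.

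The cost is wording plus one extra rate calculation from events already collected; no new data or patients are needed. The downside is that the stated precision becomes less favourable.
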